by Registered Nurse. The RAs also visit each applicable unit and asking an appropriate staff member or reviewing the patient list book to ensure EPIC was accurate. Permission to review books on the unit has been given by the Managers on each unit from which we are currently recruiting This list and corresponding admission notes will be preliminarily reviewed by the research assistant for the exclusive purpose of ruling OUT subjects 1) who do not speak English, 2) who have pre-existing diagnoses indicating cognitive impairment (ie dementia) such that consideration for enrollment in a research trial would be inappropriate, and 3) who have already been previously enrolled in this research protocol. Only relevant admission documents will be reviewed in the electronic record to determine these exclusionary criteria. We plan to do a brief review of admission notes because the project will entail screening thousands of individuals. Given the volume of inpatients at YNHH, it is impractical for research staff to approach every patient, nor is it an efficient use of their time. Review of the medical admission documents will guide research staff to offer study participation to those who are not obviously ineligible. It would enhance feasibility greatly to be able to know whether someone meets these basic potential exclusionary criteria. However, no data will be saved about the patient; instead the name of patients who are not eligible for screening will be removed from our list. The remaining individuals from the daily list will be approached by study personnel, namely Research Assistants, who will offer and administer written and verbal informed consent. After patients are consented, screened and assessed, the Research Assistant may collect data from the participant (see assessments outlined below) and the electronic medical record (concurrent medical conditions, number of previous admissions and admission medications). The Healthcare provider will not be informed by research staff about the use of substances by the patient but must rely on usual procedures and their workshop training to identify risky substance use and the need for a MI intervention. It should be noted that information about risky substance use is often noted in the patients' electronic medical records. However, lack of direct disclosure to the Healthcare provider allows us to assess the implementation of drug use detection strategies and maintains the confidentiality of information that we collect. Ideally, our training will augment information that ideally, is routinely collected. We will use the audio recording of the MI interview as evidence the intervention or referral occurred.

All Healthcare providers and Psychiatrists from CL will be issued a digital recording device. They will audio record their own MI sessions and personally consent patients for such recordings and give the recordings to the research assistant, along with identifying information that will enable the research assistant to check the patients' study enrollment status. If recordings are obtained from non-study participants (e.g., someone that was deemed ineligible or who did not provide consent), they will be immediately erased. Otherwise, they will be downloaded for storage on a secure server for later analysis.

As part of a research assistant's job, he or she will regularly send messages to all of the Healthcare providers reminding them to record any MI interventions (or CL referrals) they conduct with patients on the unit. As a back-up, additional recording devices will be conveniently placed on the units, and the administrative assistant on the CL service and research assistants will have additional recording devices that can be given to Healthcare providers and Psychiatrists from CL on demand. [name] and [name] will be apprised of the overall success of obtaining audio recorded MI interviews, although they will not be told of the success for each of the Healthcare providers or their assigned conditions. They will assist with compliance for obtaining recorded sessions if there are problems.

H. Assessments:

Data will be collected by self-report, interview questionnaires and audio recordings. The Healthcare providers will complete structured questionnaires and qualitative interviews. All of this will be coded by a subject ID rather than the individual's name. Similarly, the audio recordings will be stored as computer files on a secure server and only include subject IDs to label the interview.

The proposed project will evaluate training effects using mixed methods to gather both quantitative and qualitative data^{122,123} and be organized according to the basic structure of Kirkpatrick's widely applied four level training evaluation model.¹²⁴ Given space limitations, only instruments central to our primary and secondary outcomes or that are less familiar are described in more detail. Healthcare provider assessments will occur at baseline, during the trial, and post-trial (i.e., after their 40th assigned study-enrolled patient has been discharged from the unit). Patient assessments will occur only at baseline. Of importance, we will have several research staff trained in the ITRS and MISC 2.1 Client Language Coding System (both described below) rating MI proficiency throughout the trial to accommodate the large number of recorded sessions generated in this study.

1. Reaction level (reactions to the different implementation strategies)

- **Workshop Evaluation Form and Supervision Evaluation Forms**^{21,22,91} will evaluate the Healthcare providers' satisfaction with the workshops and supervision provided in the study.
- **Facilitators and Barriers Qualitative Interview** will be used to assess the Healthcare provider and \ perception of the facilitators and barriers of their assigned implementation strategy post-trial. Focus groups consisting of approximately 8-12 Healthcare providers and that will target the five broad domains from the Consolidated Framework for Implementation Research:⁸ (1) characteristics of the MI intervention; (2) external pressures to provide a substance abuse intervention, and specifically MI, to medical inpatients; (3) internal medical unit factors (e.g., fit within usual care, incentives, prioritization of tasks, leadership engagement, available resources); (4) characteristics of the patients; and (5) implementation processes used in the conditions including training, supervision, and availability of the CL service will be conducted immediately following their MI training. These focus groups will be audio-recorded for the purpose of utilizing information gathered for the qualitative data analysis of this study. In addition, we will assess characteristics of the health care professional (e.g., attitude, peer influence, openness to change) that have been found to impact implementation.¹²⁵⁻¹²⁷ We will also conduct key informant focus groups and/or interviews throughout the study with the Chief PA, the Director of Hospitalist Services, Unit Chiefs, and hospital clinical staff to further assess organizational barriers and facilitators. These interviews will ask many of the same questions that facilitate and impede the use of Motivational Interviewing within the Hospitalist Service and other general medical inpatient units in the hospital. These interviews will also be audio-recorded for qualitative analysis purposes.

2. Learning level (changes in knowledge and attitudes)

- **Beliefs about MI**¹²⁸ will assess the Healthcare providers' personal experiences with and beliefs about MI and perceived barriers to implementing it.
- **Motivational Interviewing Questionnaire**^{89,129} assesses Healthcare provider knowledge of MI principles.
- **Clinician Rulers**⁸⁹ assesses Healthcare provider interest, confidence, and commitment in using MI.

3. Behavior level (changes in behavior)

- **MI Uptake** will be based on the number of MI intervention sessions audio recorded by Healthcare providers and Psychiatrists from CL.
- **Independent Tape Rater Scale (ITRS)** will assess the integrity of MI delivery and the criterion level of adequate MI performance within each session collected at baseline and during the trial. The ITRS includes items that cover therapeutic strategies that are MI consistent (e.g. reflections) or inconsistent (e.g., unsolicited advice). It also has items detailing general counseling strategies (e.g., assessment of substance use) that are not unique to MI, nor antithetical to it, and interventions particular to other substance abuse treatment approaches (e.g., coping skill development). For each item, raters evaluate the practitioners for adherence (i.e., the extent of intervention delivery) and competence (i.e., the skill/quality of intervention delivery) along 7-

point Likert scales. For our primary outcomes, we will: 1) calculate mean adherence and competence scores for the two factors (fundamental and advanced MI strategies) identified in prior psychometric analyses;⁹¹⁻⁹³ and 2) determine if sessions achieve our criterion level for adequately performing MI,¹⁸⁻²² namely, at least half the MI consistent items rated average or above for both adherence and competence. Descriptive analysis of other specific and general substance abuse interventions that do not involve MI will permit identification of how Healthcare providers and Psychiatrists from CL deviate from or modify the MI intervention for the inpatient setting, an important issue when studying the implementation of evidence-based treatments in real world settings.^{125,126} We have extensive experience training ITRS raters to perform very reliable MI session process ratings.^{21,22,91,93}

4. Results level (results that occurred from the application of the new practice)

- **Motivational Interviewing Skills Code 2.1 Client Language Coding System**¹³⁰ will obtain frequency counts and strength indices of positive (change talk) and negative (sustain talk) language categories in four categories: reason (includes desire, ability, and need statements as subcategories), other (hypothetical advice to others, if-then statements about the possibility of changing, foretelling of future problems if change does not occur, problem recognition), taking steps, and commitment.

5. Healthcare provider, patient, and work environment characteristics

- **Clinician Survey**¹²⁷ collects baseline Healthcare provider demographics and background.
- **Confusion Assessment Method (CAM)** will be used to assess patients' cognitive impairment (i.e. delirium).
- **Time Line Follow Back**^{118,131} assesses patients' past month self-reported substance use.
- **Heaviness of Smoking Index**¹¹⁴ assesses 2 items from the Fagerström Test for Nicotine Dependence questionnaire¹³³ regarding amount smoked and time-to-first-cigarette of the day as a means to screen patients for smoking and likely nicotine dependence.
- **Mini-International Neuropsychiatric Inventory 5.0.0 Clinician-Rated**¹¹⁹ will be used only to generate patient drug or alcohol use diagnoses (abuse and dependence).
- **Addiction Severity Index Alcohol/Drug Section**¹²⁰ will assess the frequency, duration, and severity of alcohol and drug problems over the patients' lifetime and in the past 28 days.
- **Patient Health Questionnaire (PHQ-9)** will be used to measure patients' level of depression.
- **SF-12** will measure a patient's overall health and functioning both now and during the last 4 weeks.
- **Medical Chart Review** will be conducted to 1) obtain admission and discharge diagnoses, 2) confirm self-report of substance misuse (e.g., labs), and 3) identify possible barriers to receipt of MI that may occur after consent or assessment, e.g., onset of delirium, cardiac arrest, early release from hospital.
- **The Motivation for Change Scale**¹³⁵ uses 3 items (analogue scale coded from 1 to 100) tapping patient drug, alcohol or tobacco use likelihood problem recognition, and treatment motivation. These types of ruler-based assessments of motivation have performed as well or better than more elaborate readiness to change questionnaires in predicting behavioral intentions.¹³⁶
- **Medical Inpatient Work Index-Revised**¹³⁷ is a 15-item scale that will be adapted for use by Healthcare providers and nursing staff to assess their perception of the YNHH work environment in terms of: (1) autonomy in making patient care decisions; (2) control Healthcare providers and nursing staff have over others to promote high-quality patient care; (3) collegiality with other medical staff; and (4) administrative/managerial support. The scale has been found to be a reliable and valid index of organizational traits in U.S. general medical hospitals.^{138,139}

6. Additional assessments

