cared for 40 study-enrolled patients, whether or not the Healthcare provider has recognized the patient as a substance user and/or provided a MI intervention. These patients will be the first 40 patients administratively assigned to the Healthcare provider who are screened, consented and enrolled into the study. Screening and consent of inpatients will be done in the “background” and Healthcare provider will not be told in advance that a patient has been enrolled since this may “cue” their behavior. We will not tell the Healthcare provider of our target enrollment but rather will tell them when they have reached our “target” number. In this way, we will enroll 1200 medical inpatients who may potentially receive a MI intervention.

After completion of their caseload, Healthcare provider will have a post-trial assessment to evaluate their reaction to their assigned condition, including a qualitative interview that will determine implementation facilitators and barriers. This post-trial conversation will also debrief Healthcare provider on the overall aims of the study, individual and group performance and success in administering motivational interviewing (both in terms of the quality of individual sessions, the use of MI in appropriate cases, as well as an overview of “missed opportunities” for pts who clinically warranted the MI services but were not provided with it by their healthcare provider). This debriefing will be provided in an MI-consistent manner, supporting strengths and successes of the providers while pushing them to improve technique and accuracy.

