Primary outcomes will be 1) the percentage of MI sessions, as verified by audio recordings, conducted among each Healthcare provider 40 consecutively enrolled study patients, 2) independently rated MI adherence and competence ratings of the sessions, and 3) the percentage of sessions conducted that meet a criterion level of adequate MI performance used in MI effectiveness¹⁸⁻²⁰ and clinician training trials.^{21,22} In addition, we will calculate the relative costs and cost effectiveness of the three conditions. Secondary outcomes will be 1) independently rated strength and frequency of patient statements that favor change in the sessions (called change talk) as a proxy for patient outcomes,^{23,24} and 2) themes related to implementation facilitators and barriers identified through qualitative interviews. The YNHH hospitalist and the psychiatric CL services will work closely with research staff to implement all aspects of this project.

Initially our main unit of randomization was the PAs within the YNHH hospitalist service. The director of the hospitalist service, [name], and [name], Chief PA of the hospitalist service, both co-investigators on this proposal, have committed the participation of the PAs on the service to the protocol. The service includes 33 PAs who work during days Mon-Fri on non-critical care general medical units. There is a turnover rate of about 2 per year that nets 40 PAs during the 4-year data collection phase of the project. Prior to randomization, [name], [name] and other members of the study team will meet with the PAs during staff meetings, wherein we will describe the project and elicit interest. Thereafter, we will screen PAs for eligibility and obtain written consent for their participation. PAs will next complete baseline assessment, including an audio recorded sample of their usual manner of interviewing an inpatient with a substance use problem. Following baseline assessments, a restricted randomization procedure will be used to allocate an equal number of PAs to the three conditions (10 PAs per condition).

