Originally this study focused on training PAs because they have become very prevalent and important midlevel providers in all practice settings in U.S. medicine. PAs have been used to address current health system and societal needs for primary care¹⁰⁵ and to reduce service costs¹⁰⁶ and house staff hours as mandated by the Accreditation Council of Graduate Medical Education.^{107,108} Moreover, they spend more time interacting with their patients than physicians within the YNHH hospitalist system, and recent work has shown PAs have the interest and capacity to learn behavioral intervention strategies such as MI.⁶⁹

While our initial goal was to randomize and enroll PAs only in this study, other healthcare providers have shown interest, ability to incorporate MI into their daily schedule and proven to be ideal candidates to include as a part of our cohort.

C. Study Setting

The study will take place on the general medical inpatient units of YNHH. The internal medicine hospitalist service (where we will be recruiting PA participants) consists of 8 teams, each comprised of an attending physician and 2-5 PAs. PAs typically see patients on more than one unit and see each assigned patient 1-2 times per day. Hospitalist patients are followed by one PA and one MD from the service. The hospitalist teams cover about 160 beds/day (range = 130-210) on 13 different units excluding intensive care units. In 2010, the service was responsible for approximately 9,900 discharges. The average length of stay for patients is 4 days. The psychiatric CL is available to all attending MDs and PAs for the assessment and initiation of treatment for mental health and addiction problems. Attendings and PAs order CL services via entry into the electronic medical record, which are viewed by a CL administrative assistant and CL staff throughout the day. Consultations are typically seen within 4-8 hours of placement, depending upon the acuity and time sensitivity of the requested consult. Non-urgent consults may be seen the next day if the caseload is high.

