General medical inpatient units have a patient population characterized by very high rates of co-morbid substance use disorders typically in excess of rates found in other primary care settings.¹ Moreover, large numbers of hospitals have adopted the hospitalist model for inpatient care on medical units,¹⁰⁹ and almost all hospitals have psychiatric CL services for addressing mental health and addiction problems that fall outside the expertise of medical providers.^{17,110} This study has the potential to identify highly disseminative strategies for integrating substance abuse services into primary care in a major sector of the U.S. health care system.

The practice under study for implementation is a single 20-min MI session that we have used to train medical students and physicians^{21,89} and are currently comparing to a computerized MI approach with substance using women in outpatient primary care treatment.⁸⁷ The MI session includes six steps: (1) understand patient's view of his/her substance use and motivations for change; (2) discuss reasons for using vs. not using/cutting down; (3) provide personalized feedback about patient's substance use; (4) continue handling resistance skillfully and draw out change talk; (5) develop a change plan or present change options for later consideration; and (6) summarize and support what the patient has decided to do. Clinicians ask key questions at the conclusion of steps 2-4 to ascertain the patient's commitment to change. If the patient endorses a goal of quitting or cutting back substance use, the clinician immediately proceeds to Step 5. Thus, clinicians adapt MI to their specific patient's readiness to change, giving the manualized treatment flexibility to avoid a rigid application of MI that might undermine its effectiveness and acceptability to clinicians.^{24,46}

Healthcare providers will each receive the MI implementation strategy offered within their assigned condition. Separate workshop trainings will occur for Healthcare providers within conditions. Additional workshops will be conducted as needed if new Healthcare providers are recruited into the study. In each condition, all Healthcare provider as well as the Psychiatrists from CL in ORDER ONE will audio record their MI interviews to confirm the interviews have occurred and to permit MI integrity rating.

1. Workshop (See One)

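### Each provider is debriefed on aims, group performance and missed opportunities after their own 40th patient, without waiting for colleagues still being counted, which puts the uptake measure at avoidable risk for later finishers

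*Combined protocol and SAP*

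**What the plan says.** The Research Plan (Section V, item 3) times the post-trial contact by provider: "After completion of their caseload, Healthcare provider will have a post-trial assessment to evaluate their reaction to their assigned condition". It continues: "This post-trial conversation will also debrief Healthcare provider on the overall aims of the study, individual and group performance", and then covers success in giving MI and the patients for whom it was clinically warranted but not given. Subsection H (Assessments) fixes the time point as "post-trial (i.e., after their 40th assigned study-enrolled patient has been discharged from the unit".

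The Research Plan also keeps two things from providers while they are observed. On enrolment, "Healthcare provider will not be told in advance that a patient has been enrolled", because that might cue behaviour. On caseload, "We will not tell the Healthcare provider of our target enrollment but rather will tell them when they have reached our" target number. The uptake outcome for H1 is the percentage of each provider's 40 enrolled patients who have a recorded MI session.

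On setting, subsection C says the hospitalist service "consists of 8 teams, each comprised of an attending physician and 2-5 PAs". Allocation is by individual provider, using a restricted procedure to "allocate an equal number of PAs to the three conditions (10 PAs per condition"; no stratification by team is stated. Data collection lasts 4 years. Entry can be staggered: "Additional workshops will be conducted as needed if new Healthcare providers are recruited into the study", and item 12 (Statistical Considerations) provides for new hires to replace providers who discontinue.

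No section delays the debrief until others finish, asks finishers not to discuss it, or calls for its date to be recorded.

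**The concern.** H1 is meant to show what providers do unprompted after training. The plan protects that by hiding enrolment status and the target. It also limits performance information elsewhere: subsection G withholds provider-level success and assigned condition from two named people who help with recording compliance. The debrief has no matching limit. It gives a finisher information about the uptake measure and the groups while that finisher may still be working beside colleagues whose patients are being counted.

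If finishers talk, uptake among later finishers may depend partly on when a colleague finished, and not only on assigned condition. With 10 providers per arm, a change in a few providers' behaviour could matter. Any group figure given to an early finisher also comes before the trial is complete, and no interim release of results is planned.

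**Working it through.** The plan gives no figure on this point, so the check compares passages and adds two supporting calculations.

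**1. What the debrief could add to what an observed colleague knows**

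- *Which current patients are enrolled:* hidden. A finisher learns about their own caseload, whose last patient has been discharged. That says nothing about a colleague's current patients.
- *Target number:* withheld until reached. A finisher debriefed on individual performance could pass it on.
- *Aims:* partly known already from staff meetings and consent.
- *Group performance:* no other step is described as giving this to providers. It could be passed on.
- *Eligible patients without a recorded session count as missed:* no section says observed providers are told this. It could be passed on.

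The exposed elements are therefore the target, the group results and how uptake is counted. Enrolment status is not exposed.

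**2. Are teammates likely to be in other arms?**

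Inputs: 30 providers, 10 per arm (Research Plan), and teams of 2 to 5 PAs (subsection C). Assumption: allocation ignores team. For a team with k randomized providers,

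P(all in one arm) = 3 × C(10,k) / C(30,k).

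- k = 2: 3 × 45 / 435 = 0.310, so P(mixed) = 69%
- k = 3: 3 × 120 / 4060 = 0.089, so P(mixed) = 91%
- k = 4: 3 × 210 / 27405 = 0.023, so P(mixed) = 98%
- k = 5: 3 × 252 / 142506 = 0.005, so P(mixed) = 99.5%

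**3. How much of the caseload could fall after a teammate's debrief?**

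The documents do not give accrual pace or entry dates, so this simulation is illustrative. Assumptions: 12 months on average to reach 40 patients; all 30 providers spread over the 8 teams; debrief at the 40th enrolment; coefficient of variation of pace between providers 0 to 0.5; entry spread over 0 to 24 months. The share of the 1,200 patients seen after the first debrief in their provider's team was:

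- simultaneous entry, equal pace: 15%
- entry over 12 months, equal pace: 33%
- entry over 24 months, coefficient of variation 0.5: 53%

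This is the share open to leakage, not the share affected. A later debrief would reduce it.

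**4. Direction**

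Leakage that raised uptake in SEE ONE would narrow both H1 contrasts. Leakage into ORDER ONE, where a provider can respond simply by placing an order, could widen H1b. Leakage that raised all arms alike would lift the levels and leave the differences roughly unchanged. The documents do not favour one of these.

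**The case against.** The case against has four parts.

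*Providers already know a lot.* They hear the project described, consent to randomization, are taught to screen for risky use, are regularly reminded to record, and have a booster at 20 eligible patients. Telling a finisher that the target is reached shows that a target exists. This stands, and it makes the added disclosure smaller. It does not cover group results or how missed patients are counted.

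*The timing is looser than it looks.* The text sets an earliest point, not an immediate meeting. Section X, item 2 pays for a post-trial focus group, and subsection H mentions groups of about 8 to 12, so part of the contact may be batched. This also stands. But a batch of 8 to 12 finishers would leave 30 − 12 = 18 to 30 − 8 = 22 providers, some or all of whom could still be accruing.

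*Group performance is undefined.* Nothing says it is shown by arm. That is correct, so calling it a release of comparative results would be inference.

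*The team description applies to PAs.* The cohort now includes nurses and others on other units, and the split is not given. Late entry is conditional on need. The mixed-team and exposure figures therefore apply to providers on shared teams and rest on the stated assumptions.

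**Conclusion.** The point holds as a modest, avoidable contamination route. The plan ties the debrief to each provider's own completion and has no safeguard for colleagues still being counted, most of whose shared teams would mix arms if allocation ignored team.

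Three stronger readings are tempting but not supported:

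- *That concealment is lost.* Enrolment status, the only item the plan links to cueing, stays hidden from later finishers.
- *That the bias shrinks DO ONE and ORDER ONE against SEE ONE.* That is one possible direction among several.
- *That a loss in percentage points can be stated.* Any such figure needs assumed uptake by arm, and item 12 expects 80% of patients across conditions to receive MI. Assuming 40% in SEE ONE and 60% in ORDER ONE, for example, would require 3 × 80 − 40 − 60 = 140% in DO ONE with equal arms, which is impossible.

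Neither the size nor the direction of any bias can be determined from the documents. No sample-size figure changes. The case for acting is that the risk comes from a stated rule and costs little to remove.

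**What to change.** In the Research Plan, split the post-trial contact.

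- At each provider's completion, keep the post-trial questionnaires and the facilitators and barriers interview.
- Defer the debrief on aims, target number, individual and group performance and missed opportunities until the last provider's last enrolled patient has been discharged.
- Ask finishers not to discuss the study until then.
- Record the date of every debrief, so that any held before the change can be identified at analysis.

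This is a one-paragraph amendment. The cost is that early finishers get their feedback later, and those who have left the hospital would need it in writing. Telling a finisher that recording is no longer needed still shows that a target exists, but the current plan already discloses that.
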